This is a minimal risk study using a behavioral intervention to enhance HIV-related health behaviors and biomedical outcomes. The PI will be working with engaged staff at the University of North Carolina Global Projects Zambia (UNC GPZ) to implement the study. The proposed study uses a randomized controlled trial design (Phase II clinical trial) to test the efficacy of a couples counseling and health education intervention to change HIV-related health behaviors and biomedical outcomes (viral suppression) among pregnant and postpartum women living with HIV in Lusaka, Zambia. Our sample includes 238 heterosexual couples (n=476 individuals) recruited from the population of pregnant women living with HIV attending antenatal care at Chipata Clinic in Lusaka, Zambia. All enrolled couples (intervention and control groups) will be exposed to two group health education events. Couples in the intervention (n=119 couples) will additionally be exposed to three couples counseling visits. Biospecimen collection will take place in the form of three research-only blood draws to test viral loads among the female participants (n=238). We will also conduct face-to-face behavioral interviews using a standardized questionnaire. Recruitment and initial screening will take place during routine antenatal care (see Figure below). Local Zambian research assistants will work with nurses (relationship already established during the K99 phase) to conduct the initial screenings and recruit participants. Research assistants will arrange with interested, eligible women a convenient time and place to meet with them and their male partners (either the clinic or a private community venue) to complete the informed consent process, full screening, and enrollment. A letter will be offered to take home to the male partner explaining the study (women's HIV status will not be conveyed). Screening and informed consent will be done in separate locations for WLWH and their male partners (preferably at the same time) with gender-matched research assistants. Women with severe IPV will be offered support and referrals but will not be enrolled. Enrolled couples

will attend the first group education session (“baby shower” event) together during an upcoming weekend. Randomization into the intervention or control (n=119 couples per arm) will take place following the first group session using labeled envelopes.

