Aim 1: Compare service utilization and PMTCT outcome indicators in two study conditions	Primary outcome: female viral suppression at 24 weeks postpartum (<1000 RNA copies/ml)	Intermediate outcomes: 
 ➤ female viral suppression at 6 weeks postpartum ➤ female self-reported ART adherence (visual analog scale using 3-day, one-week, and one-month recall periods) ➤ facility birth ➤ exclusive breastfeeding to six months ➤ uptake of pediatric HIV testing (and treatment if positive) ➤ postpartum family planning 	Research-only blood draws (female partner), + Behavioral surveys	Independent t-tests and Pearson's chi-square tests; logistic regression models with generalized estimating equation; survival analysis with cumulative incidence across time, Kaplan-Meier curves, mixed-effects Cox proportional hazards models
Aim 2: Establish the effect of the	Intrapersonal mechanisms: 
 ➤ mental health 	Interpersonal mechanisms: 
 ➤ IPV past month ➤ Intimacy and trust 	Behavioral surveys	Mediation analysis with structural equation modeling

intervention on intra- and inter-personal mechanisms influencing PMTCT outcomes	
 ➤ self-esteem ➤ perceived stigma ➤ perceived partner acceptance 	
 ➤ Communication skills ➤ problem-solving skills ➤ joint decision-making ➤ Conflict resolution skills ➤ Relationship satisfaction ➤ Perceived social support ➤ Communal coping 		(SEM)
--	---	---	--	-------

2. Sample size calculation: Based on the primary outcome (viral load) and a projected 25% loss to follow-up (10% due to break-ups and 15% due to other causes), we require 238 total couples (119 couples per arm) to achieve the sample size target of 178. This target is based on a Pearson's chi-squared two-sample proportions test with a power of 0.80 and alpha of 0.05, assuming a delta of 0.20 at the 6-month follow-up between the intervention and control arms. Based on recent studies from the region,⁵⁸⁻⁶⁰ we estimate viral suppression at 6-months to be 55% in the control arm and 75% in the intervention arm. For the intermediate and mediating variables on the behavioral survey, the proposed sample size will enable us to detect a hazard ratio of 0.75, power of 0.80, and alpha of 0.05, using a two-sample comparison of survivor functions exponential test.

G. Summarize Knowledge to be Gained:

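### The stated 0.80 power for a hazard ratio of 0.75 cannot be reached for women-only survey outcomes, is unsupported for the other survey variables, and is in a metric most of them lack

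*Combined protocol and SAP*

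**What the plan says.** Section IV.F.2 sizes the trial on viral suppression at 24 weeks postpartum: "we estimate viral suppression at 6-months to be 55% in the control arm and 75% in the intervention arm", by a "two-sample proportions test with a power of 0.80 and alpha of 0.05". Allowing for "a projected 25% loss to follow-up (10% due to break-ups and 15% due to other causes", it concludes that "we require 238 total couples (119 couples per arm) to achieve the sample size target of 178".

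The next claim carries this sample size over to the intermediate and mediating survey variables: "the proposed sample size will enable us to detect a hazard ratio of 0.75, power of 0.80, and alpha of 0.05". The test named is a two-sample exponential comparison of survivor functions. No event, time origin, baseline hazard or event probability is given, and the sidedness of alpha is not stated.

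The variables concerned are in the Data Analysis Plan table (IV.F.1):

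- **Aim 1, intermediate, from the survey:** ART adherence on a visual analog scale, facility birth, exclusive breastfeeding to six months, uptake of pediatric HIV testing, and postpartum family planning. Kaplan-Meier and Cox methods are listed for Aim 1, but not tied to any named outcome.
- **Aim 2:** thirteen intrapersonal and interpersonal mechanisms, such as self-esteem, perceived stigma, communication skills and relationship satisfaction, to be analysed by mediation with structural equation modeling (SEM).

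Surveys take place at baseline and at 6 and 24 weeks postpartum. They go to both partners, but section I (Aim 2) places the intrapersonal factors among the female participants.

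**The concern.** Power for a hazard ratio depends on the number of events. A ratio of 0.75 is a modest effect and normally takes several hundred events, while this trial has 238 women and each can contribute at most one first event per outcome. The sentence also applies a survival test to variables that are mostly scores or single yes/no facts recorded at fixed visits.

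This is the plan's only statement of sensitivity for the survey-based secondary outcomes and for all of Aim 2. Section G says the study will establish mechanisms and supply data for a larger trial proposal. A reader who takes 0.80 at face value would overestimate how much a null adherence or mediator result can tell them.

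**Working it through.** **Inputs.** From IV.F.2: hazard ratio 0.75, power 0.80, alpha 0.05; 238 couples, 119 per arm; 25% loss; 178 evaluable. From IV.C: "Our sample includes 238 heterosexual couples (n=476 individuals"; after 25% loss, 476 × 0.75 = 357. The event share is not given, so it is varied as an assumption.

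**1. The primary calculation reproduces.** For 55% versus 75% at power 0.80, the two-sided two-proportion formula (pooled variance under the null) gives 88.1, so 89 per arm and 178 in total; 178 / 0.75 = 237.3, so 238. The neighbouring alpha of 0.05 is therefore two-sided.

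**2. Events needed for a hazard ratio of 0.75, 1:1 allocation.**

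- Schoenfeld, two-sided: 4 × (1.960 + 0.842)² / (ln 0.75)² = 4 × 7.849 / 0.08276 = 379.4, so 380.
- Freedman, two-sided: 385.
- Exponential test on the hazard difference, no censoring, hazards 1 and 0.75 (mean 0.875): N = [1.960 × 2 × 0.875 + 0.842 × √(2 × (1 + 0.5625))]² / 0.25² = 387 subjects, all with the event.
- One-sided: 4 × (1.645 + 0.842)² / 0.08276 = 298.8, so 299 (Schoenfeld); 303 (Freedman); 305 (exponential).

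All of these exceed 238. With censoring, the exponential test on the hazard difference (two-sided) needs 847 subjects at an assumed control event probability of 50%, 592 at 70% and 446 at 90%.

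**3. Power available.** Power = Φ(√d / 2 × 0.2877 − z), where d is the number of events and z is 1.960 (two-sided) or 1.645 (one-sided).

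| Events d | Meaning | Two-sided | One-sided |
|---|---|---|---|
| 89 | half of 178 women (assumed) | 0.27 | 0.39 |
| 119 | half of 238 women (assumed) | 0.35 | 0.47 |
| 178 | every retained woman | 0.48 | 0.61 |
| 238 | every enrolled woman | 0.60 | 0.72 |
| 357 | every retained person, partners independent | 0.78 | 0.86 |
| 476 | every enrolled person, partners independent | 0.88 | 0.93 |

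**4. Smallest detectable hazard ratio, 80% power, two-sided.** exp(−2 × 2.802 / √d): 0.70 with 238 events, 0.66 with 178, 0.55 with 89.

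**5. What 89 women per arm does deliver, 80% power, two-sided.** Standardised mean difference: 2.802 × √(2/89) = 0.42. Detectable increase in a proportion, solving the step 1 formula for n = 89: about 20 points from a control rate of 50–55%, 17 from 70%, 14 from 80% and 9 from 90%. These control rates are assumptions; the plan gives none for the survey outcomes.

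**The case against.** The strongest reply is that the sentence concerns survey variables and the survey goes to men as well. With 476 individuals all having the event, two-sided power is 0.88, and 380 / 476 = 80% event occurrence would be enough. People lost later still contribute time and events, so the 178 completers are not a strict ceiling. A one-sided test on 357 events would have power 0.86. A reader might therefore infer from the event count that the claim is impossible on any reading. The documents do not support that: the pooled reading can pass 0.80.

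It is a narrow escape. It needs near-universal events and independent partners, and the plan states neither. With an assumed within-couple correlation of 0.3, 476 people count as about 476 / 1.3 = 366, and power falls to 0.79 even if everyone has the event. A one-sided test would not match the two-sided primary calculation. None of this helps ART adherence, facility birth or the women's intrapersonal measures, where even the full 238 falls short.

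Two other strong readings also fail. One is that this is the power statement for every secondary outcome. It is not: viral suppression at 6 weeks comes from blood draws and lies outside the sentence. The other is that none of the variables has a survivor function. Pediatric HIV testing, stopping exclusive breastfeeding and family planning uptake could be analysed as time to event, and Aim 1 does list survival methods. That the mediators are continuous scores is inferred from their names and the SEM plan, since no scoring is given.

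It is also fair to say that the trial is a pilot, that this sentence does not set its size, and that nothing in the plan says null results will be read as absence of effect. That limits the harm but does not make the figure right.

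**Conclusion.** The point holds in this form. For women-only survey outcomes the stated power cannot be reached at any event rate, by any of the formulas tried, one- or two-sided: 299 to 387 events are needed against at most 238. For variables measured in both partners the claim is unsupported rather than impossible. Most of the listed variables (the SEM mediators, visual-analog adherence, facility birth) have no defined event or time, so a hazard ratio is the wrong metric for them.

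The ceilings of 0.60 and 0.48 assume 1:1 allocation, proportional hazards, one first event per woman and an event in every woman. Realistic event rates give less. The 0.27 rests on an assumed 50% event share. The primary sample size is correct and unaffected.

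**What to change.** In IV.F.2, delete the claim of 0.80 power for a hazard ratio of 0.75 on the survey variables as a group. In its place:

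- **Time-to-event outcomes.** Name each outcome that will actually be analysed by Kaplan-Meier or Cox methods, define its event and time origin, state an assumed event rate, and give the detectable hazard ratio (about 0.66 with 178 events, 0.55 with 89).
- **Continuous scores.** State that 89 women per arm detects a standardised difference between arms of about 0.42 at 80% power and two-sided alpha 0.05.
- **Binary outcomes.** Give the detectable increase over a range of assumed control rates, as in step 5. Do not quote only 20 points from 55%: that base is the viral suppression rate, and a 20-point rise cannot occur from 90%.
- **Mediation.** State that the trial is not powered for indirect effects; the 0.42 describes an arm difference on a mediator, not a mediated effect.
- **Reporting.** State that secondary and mediator results will be reported as estimates with confidence intervals.

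The cost is a short rewrite and a less favourable stated sensitivity. It needs no outcome data and no extra participants.
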